• The patient will self-administer the Sitzmarks capsule (contains 24 radiopaque markers; Konsyl Pharmaceuticals, Texas, USA) by mouth with water on Days 8,9, and 10 and will consume their usual diet during this period. The patient will abstain from using suppositories or enemas until they return on Day 11. An abdominal XR will be scheduled on Day 11

Day 11 – Site Visit 2

An abdominal XR will be obtained to determine the location and the extent of elimination

of the radiopaque markers. Patients who expel at least 80% (19 or more of the markers) have

grossly normal colonic transit. If remaining markers are scattered about the colon, the condition is

most likely hypomotility or colonic inertia. If remaining markers are accumulated in the rectum or

rectosigmoid, the condition is most likely functional outlet delay. Radiographs will be collected in

electronic format and subsequently analyzed in blinded manner by a centralized reader ([name] MD, and [name], MHA, Division of Gastroenterology and Hepatology, Mayo

Clinic). The patient will be given study medication (B) and a PAC-SYM and PAC-QOL to take

home. This will trigger randomization to treatment or placebo and to PK or no PK.

Day 14- Phone call

Patients will be asked to complete the PAC+SYM and PAC-QOL questionnaires. They

will be instructed to take the medication the following morning on an empty stomach and not to

eat anything for at least 60 minutes thereafter. Baseline complete, spontaneous bowel movements

(CSBM) will be calculated from the diaries at the 14 day phone call as CSBM/entries x

7.Baseline PAC-SYM and PAC-OOL and baseline ease of passage and consistency will also be

obtained at this time-point.

PERIOD 3.2 (Stage 2): Multiple doses

Safety, tolerability and pro-kinetic effect of orally administered multiple-dose ENT-01 in

Sentinel Group followed by Remaining Cohort

Cohort 2 (40 patients, of which 10 comprise the sentinel group):

Duration: 17-19 days

The purpose of this period is to demonstrate the continued pro-kinetic effect beyond that

of a single-dose, to confirm the effective pro-kinetic dose for each individual and to establish the

safety, tolerability and PK of multiple doses of ENT-01. A pro-kinetic dose is defined as the dose

that results in a spontaneous, complete stool on at least two of the three dosing days. Once the

pro-kinetic dose is established, and assuming there are no safety concerns, each patient will be

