CP1001 v0.9, Version Date: 27JUL2017

[figure not shown]
31

kept on that fixed dose for a further 2-4 dosing days (3 days if it falls on a Saturday, 4 days if it falls on a Sunday).

The sentinel group will be a group of 10 patients who did not participate in Stage 1. Patients will be given three consecutive doses of the dose which was found to be safe and tolerable in everybody (STDE) and effective in at least some patients in Stage 1 (75 mg in schematic) at home. Patients will self-administer the study medication *daily* for 3 doses (3 days at each dosing level). The dose will be taken upon awakening on an empty stomach along with 8 oz. of water simultaneously to dopamine). The patient will not be allowed to ingest any food for at least 60 minutes after study medication. The daily diary will be completed and results verbally transmitted and emailed to the study coordinator every evening including on week-end days and entered into the electronic data capture system the same night or first thing in the morning. The coordinator will check in with the patients daily, at the end of the day and determine whether there have been any adverse events or CSBM. If the patient has not produced a CSBM within 24 hours of a dose, on at least two of the three days at a given dose, then the patient will be told to proceed to the higher dose of STDE+25mg (eg. 100mg qd) and also to use a suppository followed by an enema if necessary on the evening of the third day (See rescue diagram below). At the end of the second dosing period (100mg for 3 days), the same criteria will be applied to make a determination as to whether to proceed to STDE+50mg (e.g. 125 mg qd) or not. The incremental dosing will continue up to the consistently clinically effective (pro-kinetic) dose, or to the DLT, whichever comes first. Patients who do not have pro-kinetic effect at DLT will be treated with the highest dose at which they did not have a DLT, if it is at least the STDE dose; if the DLT occurred at the STDE dose, then the patient will be terminated. Should a pro-kinetic response not occur at 175 mg, patients will take 175 mg for the 2-4 additional fixed-dose dosing days and 6 randomized dosing days (assuming randomization is to treatment). DLT will be the dose inducing repeated vomiting or diarrhea within 24 hours of dosing. The lowest dose producing a CSBM on 2/3 consecutive doses will be noted as the pro-kinetic dose (LSTDEi i.e. consistently clinically effective safe and tolerable dose for that particular individual). Patients will be kept on the lowest dose producing a pro-kinetic effect for another 2-4 days prior to randomization in Period 4. The Enterin CMO will review the stool diaries prior to randomization to ensure dosing adequacy. PAC-QOL and PAC-SYM will be repeated prior to randomization at Visit 3. CSBM during the fixed dose period will

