4.6 Concomitant Medication

- Preventive laxatives will be discontinued during the run-in period. Throughout the study,
 patients will be allowed to take constipation *rescue medication on demand*, and only if
 they have not had a bowel movement in three consecutive days.
- In stage 1, rescue medication (laxative, bulking agent, softener, suppository) can be taken as needed and as stated above, and noted in the stool chart. Rescue medication cannot be taken during the 24 hrs before or after study medication. Any bowel movement produced within 24 hours of rescue medication will not be counted.

In Stage 2, rescue medication (Dulcolax suppository and/or enema) can be taken on demand during the run-in period as stated above and noted in the stool diary. During the dosing period, rescue medication is taken on the evening of the third dose at any given level if a stool has not been produced in response to three days of study medication. Enterin CMO should be consulted for any questions related to rescue medication. Rescue medications will be recorded in the daily diary. Bowel movement produced within 24 hours of rescue medication will not be counted as either spontaneous bowel movement or complete spontaneous bowel movement.

- In both stages, protein pump inhibitors will be discontinued during the run-in period and reinstated during the wash-out period.
- Benzodiazepines, hypnotics, other sedatives, barbiturates, and opiates will not be allowed.
 All medications shall be reviewed and dis/approved by the investigator on a case-by-case basis.
- Selective serotonin reuptake inhibitor (SSRI), SNRI, tricyclic antidepressants anticholinergics, anti-histamines and anti-psychotics are permissible at stable doses.
- Dopamine agonists and amantadine will be allowed if on a stable dose for at least 4 weeks preceding the study.
- Deep brain stimulation is allowed at the PI's discretion.

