 - a. Run-in and washout period: calculation will be based on all diaries in Run-in and Washout periods (excluding the first day diary in the period).

$$\text{Days using rescue meds per Week} = \frac{\text{Sum of days using rescue meds}}{\text{Number of Diary Days}} \times 7 \text{ days}$$

- b. Treatment period: calculation will be based on diaries on dosing days.

$$\text{Days using rescue meds per Week} = \frac{\text{Sum of days using rescue meds}}{\text{Number of Dosing Days}} \times 7 \text{ days}$$

These first two parameters will be treated as categorical variables while other parameters will be treated as continuous variables.

Stage 2 Pharmacodynamics Parameters:

- CSBM days per week for each dosing period is defined as:

$$\text{CSBM Days per Week} = \frac{\text{Sum of days with CSBM w/o rescue meds within 24 hours}}{\text{Number of Diary Days}} \times 7 \text{ days}$$

- CSBM episodes per week for each period is defined as:

$$\text{CSBM episodes per Week} = \frac{\text{Sum of daily CSBM episodes w/o rescue meds within 24 hours}}{\text{Number of Diary Days}} \times 7 \text{ days}$$

where daily CSBM episodes = $\begin{cases} \# \text{ of CSBM occurrences w/o rescue meds within 24 hrs for each diary day} \\ 0 \text{ if none CSBM w/o rescue meds within 24 hrs for each diary day} \end{cases}$

- SBM days per week for each dosing period is defined as:

$$\text{SBM Days per Week} = \frac{\text{Sum of Days with SBM w/o rescue meds within 24 hrs}}{\text{Number of Diary Days}} \times 7 \text{ days}$$

- SBM episodes per week for each period is defined as:

$$\text{SBM episodes per Week} = \frac{\text{Sum of Daily SBM Episodes w/o rescue meds within 24 hrs}}{\text{Number of Diary Days}} \times 7 \text{ days}$$

where Daily SBM Episodes

$$= \begin{cases} \# \text{of SBM occurrences without rescue meds with 24 hours for each day diary} \\ 0 \text{ if none SBM without rescue meds for each day diary} \end{cases}$$

- Average ease of passage for each period is defined as

$$\text{Average ease of passage} = \frac{\text{Sum of ease scale w/o rescue meds within 24 hrs}}{\text{Number of BMs w/o rescue meds without 24 hrs}}$$

- Average stool consistency for each period is defined as

$$\text{Average stool consistency} = \frac{\text{Sum of stool consistency w/o rescue meds within 24 hrs}}{\text{Number of BMs w/o rescue meds within 24 hrs}}$$

- Days using rescue meds (i.e., laxative/suppository/enema) per week for each period is defined as

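### In Stage 2 dose escalation, evening rescue plus the 24-hour no-count rule blocks most of the first day at the next level, which lowers the chance that an effective dose is recognised; two protocol sections also disagree on who is rescued

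*Protocol*

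**What the plan says.** Protocol section 3.1, Period 3.2, gives three consecutive daily doses at each level, taken on waking, with no gap between levels. A pro-kinetic dose is one "that results in a spontaneous, complete stool on at least two of the three dosing days", and the dose carried forward is fixed accordingly: "The lowest dose producing a CSBM on 2/3 consecutive doses will be noted as the pro-kinetic dose". A patient who "has not produced a CSBM within 24 hours of a dose, on at least two of the three days at a given dose" is told to go to the higher dose and "also to use a suppository followed by an enema if necessary on the evening of the third day".

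Protocol section 4.6 sets the same time of day but a different condition: "rescue medication is taken on the evening of the third dose at any given level if a stool has not been produced" over the three days of study drug. It also sets the no-count rule for Stage 2: "Bowel movement produced within 24 hours of rescue medication will not be counted as either spontaneous bowel movement or complete spontaneous bowel movement".

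SAP section 4.4.1 applies the same exclusion to the Stage 2 stool variables. The numerator of CSBM days per week is "Sum of days with CSBM w/o rescue meds within 24 hours", and the denominator is the number of diary days. SAP section 4.4 uses all diaries of each dosing period.

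Stage 1 differs. Section 4.6 bars rescue in the 24 hours either side of a Stage 1 dose. Stage 2 has no such provision.

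**The concern.** Rescue on the evening of the third day opens a 24-hour window that closes on the evening of the first day at the next level. The new dose is taken that morning, so the waking hours that follow it fall inside the window. No visible text exempts that day, adds a day or shortens the denominator.

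Period 3.2 exists to find each individual's lowest effective dose (LSTDEi), which then feeds the fixed-dose assessment. If the first day at a level is largely blocked, a level that works is more likely to be scored as a failure, and the CSBM rate reported for that level is too low. The last level can also be touched. Patients without a response at the top dose stay on it for as few as two fixed-dose days, and rescue after that failed level would block part of the first of them.

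Separately, section 3.1 sends every patient who fails 2 of 3 to rescue, including one with a single CSBM or with incomplete stools only. Section 4.6 confines rescue to patients with no stool. Two sites can each follow the protocol and run different effective titration rules.

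**Working it through.** **1. The plan's own figure.** The only Stage 2 design calculation is the exact binomial test against 0.10 (Protocol 10.1.2, SAP 2.2). With an upper tail of at most 0.025:
- n=34: reject at 8 or more successes, tail 0.0169, power 81.2% at 0.29.
- n=40: reject at 9 or more, tail 0.0155, power 79.1% at 0.27.
- Drop-out: 34/(1−0.15) = 40.

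The stated 80% reproduces and does not depend on this point. The documents give no operating characteristic for the 2-of-3 rule.

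**2. Timeline (clock times assumed).** Take a suppository at 8 pm on the third day and the next level's first dose at 7 am. The window closes at 8 pm on that first day, so 13 of the 24 hours after the dose are uncountable. The other 11 hours, mostly overnight, can still count, because section 3.1 credits a CSBM within 24 hours of a dose.

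**3. Chance of passing a level.** Let p be the daily CSBM probability, with independent days, and let f be the share of first-day CSBMs that stay countable. Both are assumptions.
- All three days countable: 3p² − 2p³.
- First day reduced: p² + 2p(1−p)·fp.

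| p | Unblocked | f = 0 | f = 0.2 |
|---|---|---|---|
| 0.5 | 0.500 | 0.250 | 0.300 |
| 0.667 | 0.741 | 0.444 | 0.504 |
| 0.8 | 0.896 | 0.640 | 0.691 |

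At f=0 the loss is 2p²(1−p). It is 6 points at p=0.2 and peaks at p=2/3: 2 × 4/9 × 1/3 = 0.296, about 30 points.

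**4. By-dose rate.** With three diary days, the expected CSBM days per week are 7p unblocked and 7p(2+f)/3 blocked. At p=0.5 that is 3.5 against 2.3 (f=0) or 2.6 (f=0.2).

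**5. Assigned dose, July 2017 range (75–175 mg).** Simulation of 400,000 patients with assumed p of 0.15, 0.67, 0.70, 0.75 and 0.80 at the five levels; a patient who passes none is assigned 175 mg:

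| Rescue trigger and first-day loss | Assigned second level | Mean dose (mg) |
|---|---|---|
| No blocking | 69.9% | 106.0 |
| Section 3.1, f=0 | 42.0% | 120.9 |
| Section 3.1, f=0.2 | 47.6% | 117.3 |
| Section 4.6, f=0, no incomplete stools | 51.9% | 112.4 |
| Section 4.6, f=0, incomplete stools on 30% of days | 63.8% | 108.1 |

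**6. Assigned dose, amended range (100–250 mg, SAP 2.1).** Suppose the drug already works at the first level, which is unblocked. Use the section 3.1 trigger with f=0. Mean dose is 100 + 25 × the sum, for k = 1 to 6, of the chance of failing the first k levels.
- p=0.5, unblocked: sum of 0.5^k = 0.984, mean 125 mg; no level passed 0.5^7 = 0.8%.
- p=0.5, blocked: 0.5 × (1−0.75^6)/0.25 = 1.644, mean 141 mg; no level passed 0.5 × 0.75^6 = 9%.
- p=0.7, unblocked: 0.216 × (1−0.216^6)/0.784 = 0.276, mean 107 mg.
- p=0.7, blocked: 0.216 × (1−0.51^6)/0.49 = 0.433, mean 111 mg.

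**The case against.** A reader might infer that the 2-of-3 rule becomes 2 of 2 and that patients are pushed above their true dose. The documents do not support that as a general statement. The interval from the first evening to the next waking still counts under section 3.1. All of the first day is lost only if the exclusion is applied by whole diary day, or if a later repeat suppository or enema extends the window. The visible diary example shows dates without clock times, but its header is broken, so this cannot be settled. The first level is never blocked by this rule, and over-escalation becomes more likely, not certain.

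A reader might also take the July 2017 cap of 175 mg, block every level from 100 mg up at p=0.5, and find the mean dose rising from 122 to 143 mg and the share passing no level from 0.5^4 = 6% to 0.75^4 = 32%. Those figures need the section 3.1 trigger, a first day wholly lost, a rescued failure before 100 mg, and a dose range that the February 2018 amendment replaced.

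The text on rescue after three days without a stool within section 3.1, Period 4, is not a third conflicting trigger. It governs the randomized period.

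Three further objections have force. The rescue diagram cited in Period 3.2 was not available for review and may settle some detail, although the Period 4 text cites a figure for the same third-evening timing. Excluding post-rescue stools is sensible in itself, because it avoids crediting rescue to the drug. The primary endpoint uses fixed-dose days, and patients who pass a level do not trigger the failure rescue just before them. What remains is the overlap with the next level's first day, the unchanged rule and denominator, and the contradiction on who is rescued.

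**Conclusion.** The point holds in a limited form. By the documents' own timing, the daytime after the first dose of any level that follows a rescued failure cannot contribute a CSBM, while the decision rule and denominator stay the same. The chance that an effective level passes falls from 0.50 to 0.25–0.30 at p=0.5 and from 0.90 to 0.64–0.69 at p=0.8. By-dose CSBM rates at those levels are biased downward, and over-escalation may be more likely.

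The effect on assigned dose is smaller under the section 4.6 trigger (108–112 mg against 106 mg unblocked in the example) and when the first level already works (107 to 111 mg at p=0.7 in the amended range). All sizes rest on independent days, a p that rescue does not alter, and values of p and f that the documents do not give.

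Sections 3.1 and 4.6 contradict each other on who is rescued, whatever the modelling assumptions. The primary power calculation is unaffected.

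**What to change.** In the protocol, reconcile the Period 3.2 text of section 3.1, section 4.6 and the rescue diagram with each other, and with the 24-hour no-count rule as it bears on the 2-of-3 decision. The clinical rule, including whether all decision days must be countable, is for the sponsor.

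In the SAP:
- Flag every dose-level and fixed-dose day that falls in a post-rescue 24-hour window, and state whether the window is applied by clock time or by diary day.
- Add a sensitivity by-dose summary of CSBM and SBM that removes flagged days from numerator and denominator.
- Report how many escalation decisions included a blocked first day.

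The cost is a clarifying amendment and one derived flag from diary data already collected. The added summaries will rest on fewer days.

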Each dose period will be staggered, so that patients 1-2 will be administered a single dose of the drug at the lowest dose of 25mg. Once 24 hours have elapsed, and provided there are no safety concerns, they will be sent home and brought back on day 4-8 for the next dose. During the days the patients are home, they will complete the daily diaries and e-mail them to the study coordinators. The study coordinators will call the patients every other day starting on the day following discharge for each dose and determine with the patient if a suppository or laxative is needed, as well as inquiring about any adverse events. Diary information will also be discussed with the patients during the telephone calls. Patients 3-10 will be dosed after the first two patients have been observed for 72 hours, i.e. on Day 4. Patients 1-2 will also be brought back on Day 4-8 and will be given a single dose of 50mg. Once another 24 hours have elapsed and provided there are no safety concerns, they will all be sent home and instructed to return on Day 7 for the next dosing level. This single dosing regimen will be continued until each patient has been given a single dose of 200mg or has reached a dose limiting toxicity (DLT). DLT will be the dose which induces repeated vomiting, diarrhea, abdominal pain or symptomatic postural hypotension within 24 hours of dosing. Maximum tolerated dose (MTD) will be the highest dose for which there was no more than 1 DLT endpoint (refer to Section 9.8, DLT endpoint criteria). A review of safety, tolerability and adverse events will occur prior to administration of each dose level and at the end of Period 2 with DSMB. After the last dose of medication, BDI, MMSE, Trail-making A and B, NMSQ, UM-PDHQ, PFS-16, RBDQ, PDSS, PAC-SYM and PAC-QOL will be administered.

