MTD: Maximum Tolerated Dose **ID: Intolerant Dose** No prokinetic response MTD ID Day10 Day13 Subject Day 1 Day4 Day7 Day16 Day19 Day22 Day 25 25mg 50mg 100mg 75mg >125mg 150mg 175mg 2 25mg 50mg 75mg 100mg 125mg 150mg 175mg 200mg Stage 1 Period 2.1 3 50mg 75mg 100mg 125mg 150mg 175mg 25mg (COHORT 1) 4 25mg 50mg 75mg 100mg 125mg 150mg Single dose 125mg 5 25mg 50mg 100mg 150mg 75mg 175mg 200mg safety, 50mg 100mg 125mg 6 75mg 25mg tolerability and 50mg 100mg 7 25mg 75mg 125mg 150mg 175mg identification of 8 25mg 50mg 75mg 100mg 125mg 150mg prokinetic dose 50mg 100mg 125mg 150mg 25mg 75mg → 175mg 200mg 10 25mg 50mg 75mg 100mg 125mg 150mg 175mg 200mg STDE DOSE in this example is 75 mg, that being the lowest dose that is safe and tolerable in all subjects and has a prokinetic effect in at least some

Schematic for Stage 1, Period 2.1: Hypothetical dosing regimens

Pharmacokinetics: Timed blood samples (5.0 mL) will be collected into Li-Heparin treated tubes for analysis of ENT-01 plasma concentrations. Plasma samples will be obtained for pharmacokinetics before dose administration and at 1, 2, 4, 8, and 24 hours.

Once collected, PK samples will be stored in a -20°C or -70°C freezer until time of shipment. Labels and appropriate shipping materials will be provided to sites. The concentration of study drug will be determined from the plasma samples using a validated analytical method. Details of the method validation and sample analysis will be included with the final clinical study report.

Individual stopping criteria:

The complete panel of Blood Chemistries described in Appendix 1 are to be drawn 24 hours after each dose. Results will be reviewed the evening before the following dose. In addition, any patient with at least 1 DLT endpoint (see **Section 9.8**), or with another non-DLT gastrointestinal AE > grade 3 that is at least possibly attributable to ENT-01, or elevated AST, ALT, or total bilirubin > 3x ULN or a reduction of body weight of 10% or more from baseline will be terminated. ENT-01 has very little systemic absorption, and hence adverse events are expected to be within the gastrointestinal system.

Refer to Section 9.12 for Adverse Event Grading and to Section 9.8 for DLT Endpoint

Criteria.

Go/No-go decision:

Safety: We are assuming that no more than 1 patient out of ten (10%) will have an adverse event

of grade 4 or 5 that is at least possibly related to ENT-01 in dose levels thought to be below

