
be calculated as CSBM/#fixed dose days x 7. The primary end-point is obtained by comparing this number to the baseline CSBM obtained at the end of the run-in period.

2: SUPPOSITORY/ENEMA RESCUE USE DURING DOSE ESCALATION IN STAGE

Patients will wear I-Buttons starting with the lowest dose (e.g. 75 mg) and will remove them on day 5 of the wash-out period. The remaining 30 patients will start on STDE (e.g. 75mg) as soon as they have completed the Run-in Period and will follow the same incremental dosing regimen until they reach their LSTDEi or maximum tolerated dose. These regimens and adjustments are shown in the schematic below.

Once the LSTDEi has been established, each patient will remain on that dose for two to four additional days prior to randomization in Period 4 (5 to 7 consecutive days on prokinetic dose)

N.B. Primary end-point is obtained by comparing stool diary at this point with baseline diary on rescue medication at the end of the run-in period.

Visit 3 for non-PK patients (Day before Randomization).

Non- PK patients will come to the site for a visit to return any unused study drug (B), receive 6 daily doses of randomized drug (A or C), Sitzmarks capsules and will complete all the questionnaires listed below. They will be sent home with 6 daily doses of A or C and Sitzmarks capsules and will return for Visit 4 on Day 6 of randomization to complete all the questionnaires.

Go/No-go decisions:

Safety: We are assuming that no more than 1 patients out of forty (2.5%) will have an adverse event of grade 4 or 5 that is at least possibly related to ENT-01 in this Stage. Should there be more than 1 patient with an AE grade 4 or 5 that is at least possibly related to Enterin-0 in this cohort

of 40 patients, the study will be put on an immediate safety hold until an emergency DSMB meeting can be held to evaluate the study for possible discontinuation.

Tolerability: We are assuming that all patients will exhibit a pro-kinetic effect at a dose lower than DLT and less than or equal to 175mg. Patients reaching DLT before a pro-kinetic effect will be terminated if the highest dose for the patient without a DLT was the STDE dose. Otherwise the patient will be treated at the highest dose at which they did not experience a DLT if they are randomized to the treatment arm (or will receive the equivalent dose of placebo).

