Efficacy: We are assuming that a consistent pro-kinetic effect will be observed in all patients. Patients in whom a pro-kinetic effect is not observed at the maximum dose of 175mg will continue to take 175mg for another 2 days and enter the randomized period. If they are randomized to treatment, they will be given 175mg/day for the 6 randomized dosing days.

Individual stopping criteria:

Patients who reach DLT before a pro-kinetic effect, exhibit LFT elevation above 3xULN, have a 10% or greater reduction in body weight or those with a non-DLT gastrointestinal AE > grade 3 within 24 hours of taking ENT-01 that is at least possibly attributable to ENT-01 will be terminated.

Pharmacodynamics: Patient will record bowel movements, ease of passage, consistency and suppository usage in the daily diary throughout the Period and transmit the information to the coordinator every evening.

Sleep assessment: Patients will wear the I-Button throughout the dosing period and remove it only during bathing periods.

STDE DOSE in this example is 75 mg, that being the lowest dose that is safe and tolerable in all subjects and has a prokinetic effect in at least some LSTDEi is the lowest safe and tolerable dose that produces a prokinetic response reached by an individual in at least 2 of 3 days at that dose Subject Day1 Day2 Day3 Day4 Day5 Day6 Day7 Day8 Day9 Day9 Day1 Day12 Day12 Day13 Day14 Day15 Day16 Day17 Day18 Day19 Day20 Day21 Day22 100mg 100mg 100mg 100mg 100mg 100mg 100mg ng 100mg 100mg 100mg 100mg 100mg 100mg 100mg 100mg 125mg 125mg 125mg 125mg 125mg 125m 150mg 150mg 150mg 150mg 150mg 150mg 150mg COHORT 1, 100mg 100mg 100mg 100mg 100mg 100mg Stage 2. SENTINEL PERIOD 3.2, g 125mg ng 150mg 150mg 150mg 150mg 150mg 150mg ROUP N=10 (COHORT 1) 75mg | 75mg | 75mg Safety and tolerability of 3 day dosing. and extension to a total of 5 COHORT 2 doses GROUP, N=32 **RUN-IN PERIOD FOR SUBJECTS 11-40** Day 23 Day24 Day25 Day26 Day27 Day28 Day29 Day30 Day31 Day32 Day 33 Day34 Day35 Day36 Day37 Day38 Day39 Day40 Day41 Day42 Day43 Day44 COHORT 2 GROUP, N=32 11-40

Schematic of Stage 2, Period 3.2 with hypothetical dosing regimen

DSMB: The DSMB will meet at the end of the fixed dose period for the ten sentinel patients.

LSTDEI LSTDEI LSTDEI LSTDEI

PERIOD 4

(Stage 2): Randomized, double-blinded treatment period to determine the effect of orally administered ENT-01 on pharmacodynamics and motility.

Duration: 6 days

Visit 3 for PK patients (Day 1 of randomization):

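### The Stage 2 escalation rule counts only vomiting and diarrhea as dose-limiting, while protocol section 9.8 and SAP 4.3 also count Grade 2 abdominal pain and postural hypotension

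*Protocol*

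**What the plan says.** Protocol section 3.1, Period 3.2, has patients dose themselves at home for three days per level. They step up by 25 mg until a pro-kinetic response or a DLT, whichever is first. In that paragraph, "DLT will be the dose inducing repeated vomiting or diarrhea within 24 hours of dosing". The DLT stops escalation, sets the dose for a patient without a pro-kinetic response, and ends participation if it occurs at the starting (STDE) dose.

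Other places define the term more widely:

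- The parallel Stage 1 sentence (Period 2.1) reads "DLT will be the dose which induces repeated vomiting, diarrhea, abdominal pain or symptomatic postural hypotension within 24 hours of dosing". It gives no grades.
- Section 9.8 lists recurrent vomiting, recurrent diarrhea, moderate abdominal pain and postural hypotension. All are labelled Grade 2, and the last has alternative blood pressure limits. The section is not restricted to a stage.
- SAP 4.3 gives the same four and adds liver enzyme and weight criteria for analysis. SAP 7.8.6 applies the list from Stage 1 to the end of Stage 2 fixed dosing.

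Protocol section 10 and SAP 2.1 describe the Stage 2 dose as the pro-kinetic one reached without a DLT.

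**The concern.** Tolerability is part of the primary Stage 2 objective, and the DLT is the event that sets an individual's dose. If the dosing text uses a shorter list than the analysis text, one event can be a DLT in the report and not a reason to stop stepping up at home. A patient with moderate abdominal pain at 100 mg and no pro-kinetic response would go to 125 mg under Period 3.2, whereas under section 9.8 escalation would stop. The event is foreseeable: protocol section 1.3 names cramps among the expected adverse events. Stage 1 doses were followed by 24 hours of clinical-unit monitoring; Stage 2 escalation is supervised by telephone.

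**Working it through.** This is a comparison of definitions; the plan states no figure to reproduce.

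**1. Categories.** Section 9.8 has 4 clinical categories and the Period 3.2 sentence has 2, so 4 − 2 = 2 are missing: abdominal pain and postural hypotension.

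**2. What the rule governs (July 2017 range, 75 mg start).** Levels: (175 − 75)/25 + 1 = 5, so 4 upward steps. Escalation days: 5 × 3 = 15. Adding 2 to 4 fixed-dose days gives 17 to 19, which matches the duration stated for Period 3.2.

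**3. Does another Stage 2 rule close the gap?**

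- *Individual stopping criteria.* The list opens "Patients who reach DLT before a pro-kinetic effect, exhibit LFT elevation above 3xULN" and goes on to weight loss and non-DLT gastrointestinal events above Grade 3. Postural hypotension is not gastrointestinal. In section 9.7 the abdominal pain scale ends at Grade 3, so no grade of pain lies above 3. If the sign was meant as at least Grade 3, severe pain is caught and Grade 2 pain is still missed.
- *Maximum tolerated dose.* The remaining 30 patients escalate "until they reach their LSTDEi or maximum tolerated dose". That term is defined only in Stage 1, as "the highest dose for which there was no more than 1 DLT endpoint". It refers to section 9.8 but allows one DLT endpoint. The rule that stops "any patient with at least 1 DLT endpoint" belongs to Stage 1.
- *Blood pressure limits.* In the Stage 2 schedule (Appendix 2), no vital signs fall between the start of dosing and Visit 3, which comes after escalation. During escalation postural hypotension can only surface as reported symptoms.
- *Judgment and oversight.* The fixed dose continues "assuming there are no safety concerns". There is also a daily adverse event call, withdrawal on medical-monitor or investigator judgment (section 4.5), DSMB review, and a hold after more than one possibly related Grade 4–5 event. These protect patients, but none is a dose rule for a Grade 2 event.

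**4. What follows a DLT before a pro-kinetic effect (example: STDE 75 mg).**

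| Protocol text | DLT at 100 mg | DLT at 125 mg |
|---|---|---|
| Period 3.2, escalation paragraph | continue at 75 mg | continue at 100 mg |
| Section 10 | continue at 75 mg | continue at 100 mg |
| Period 3.2, go/no-go for tolerability ("will be terminated if the highest dose for the patient without a DLT was the STDE dose") | terminated | continue at 100 mg |
| Period 3.2, individual stopping criteria | terminated | terminated |

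The Period 4 text adds another termination rule, for a tolerability limit below a clinically effective dose, and it is unclear which dose is the comparator. Widening the DLT list makes this conflict apply to more events.

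**The case against.** The best defence is that the Period 3.2 sentence is shorthand. Section 9.8 is the protocol's general list of DLT criteria, the word repeated needs its counts to have meaning, and section 10 uses one term for both stages. This is possible. But the sentence states its own definition without citing 9.8, and the pointers to 9.8 for the DLT in the supplied text sit in Stage 1 material. Someone working from the Period 3.2 instructions sees two categories.

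The narrowing might also be deliberate, since the synopsis and section 2.1 list tolerability endpoints for Stage 1 only. No document says whether it was intended. If it was, the SAP needs to match it.

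Some of the defence stands. Symptomatic postural hypotension under 9.8 must be severe enough to need medical intervention, so it is likely to reach the investigator anyway; abdominal pain is the less protected category.

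A reader might also infer that the DLT table will show DLTs at the doses labelled safe and tolerable. SAP 7.8.6 does not support that, because it summarises Stage 2 DLTs for the treatment period and not by dose. SAP 7.8.1 does tabulate adverse events by dose level, with summaries by maximum grade, so pain or dizziness at a given dose would be visible there.

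**Conclusion.** The inconsistency is real and sits in operative text. Two of four DLT categories are absent from the rule that governs up to four upward steps over 15 days at home, and no other Stage 2 rule supplies them for Grade 2 events. The two definitions can give the same patient different doses. It should be corrected.

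The conclusion rests on reading the July 2017 text as written. It is not a finding that patients were unprotected or harmed: the safeguards based on judgment are real, and the documents give no basis for estimating how many patients would be affected. Nor do they show that stepping down is the right consequence of a DLT, because the protocol states both stepping down and termination without ranking them. It may be tempting to extend the point to the amended 100–250 mg range, since SAP 2.1 reports no changes beyond the dose range and the removal of randomization. The amended protocol is not supplied, so nothing is claimed for it.

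**What to change.** 1. In Period 3.2, replace the DLT sentence with: *DLT is any section 9.8 criterion, at Grade 2 or higher, within 24 hours of dosing.* The words *or higher* matter because the counts in 9.8 are capped (3–5 and 4–6 episodes). State that on escalation days postural hypotension is judged on symptoms reported at the daily call.
2. Reword the Period 3.2 individual stopping criteria so that termination applies to any possibly related gastrointestinal event above Grade 3, whether or not it is also a DLT. Without this, the wider DLT would take severe vomiting or diarrhea out of the non-DLT clause. If step-down were then adopted, Grade 4 diarrhea at 125 mg could lead to continued dosing at 100 mg.
3. Separately, choose one consequence for a DLT before a pro-kinetic effect, either step down or terminate. State it identically in the Period 3.2 escalation paragraph, the go/no-go text, the stopping criteria, Period 4 and section 10.

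If a narrower Stage 2 DLT was intended, the alternative is to say so with a reason and align SAP 4.3 and 7.8.6 with it.

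The cost is protocol wording, with no new visits or data, but item 3 needs a decision by the sponsor. Some patients may be held at a lower dose or stopped earlier than Period 3.2 now allows.
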